
Safety Evaluation:
	
Safety will be evaluated by tabulations of adverse events (AEs), Cutaneous Safety Assessments for dryness and scaling, assessments for scores (erythema and telangiectasia) and Patient Global Impression of Treatment Side-Effects (PGI-SE) will be presented with descriptive statistics at Baseline and at the scheduled study visits. Frequencies and percentages for each outcome category will be included in these statistics.

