- Patient Global Impression of Symptom Severity (PGI-S) at Week 12
- Patient Global Impression of Treatment Satisfaction (PGI-TS) at Week 12.
- A set of cumulative distribution function (CDF) curves will be generated to allow for the evaluation of within-person change by treatment group. Specifically, 5 plots will be generated showing the change from baseline to Week 12 [and/or other, earlier time points if so desired] by the cumulative percent of subjects for each of the treatment arms (change on the x-axis will be expressed as absolute change) on:
 - PAPSS total scale scores;
 - PAPSS item 1 (burning) scores;
 - PAPSS item 2 (itching) scores;
 - PAPSS item 3 (redness) scores; and
 - PAPSS item 4 (bumps) scores

- **The safety objective of this pivotal study is:**

The safety objectives of this study are to determine the nature, severity and frequency of the adverse event rate, the Cutaneous Safety Assessment and the Local Tolerability Assessment of S5G4T-1 compared to the vehicle.

The safety endpoints to be assessed include the following:

- Adverse events (AEs), including serious adverse events (SAEs) occurring at any time during the trial.
- Investigator Cutaneous Safety Assessment and Local Tolerability Assessments score at any time during the trial.

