16.2. Local Tolerability Assessments

The evaluator will assess local application site tolerability by rating the itching and burning/stinging at the Baseline visit and site visits at Weeks 2, 4, 8 and 12 (End of Study) or unscheduled visits. The evaluator will determine the score for each of these variables by asking the patient to grade their experience over the **past 24 hours**. The definitions of grades provided in [Table 5](#) will be applied to these evaluations. The Local Tolerability Assessment evaluations of itching and burning/stinging will be made by the investigator at the time of the visit.

Table 5: Local Tolerability Assessment Scale

Grade	Description
Itching	
0 – None	No itching
1 – Mild	Slight itching, not really bothersome
2 – Moderate	Definite itching that is somewhat bothersome
3 – Severe	Intense itching that may interrupt daily activities and/or sleep
Burning/Stinging	
0 – None	No burning/stinging
1 – Mild	Slight burning/stinging sensation; not really bothersome
2 – Moderate	Definite warm, burning/stinging sensation that is somewhat bothersome
3 – Severe	Hot burning sensation that causes definite discomfort and may interrupt daily activities or sleep

Application site reactions (itching and burning/stinging) are not to be recorded as adverse events unless they result in either:

- The temporary discontinuation of the study product.
- The discontinuation of the patient from the study.
- The use of a new concomitant medication in order to treat this event.

Any other application site reaction not listed above should be recorded as adverse events in the source document and eCRFs.

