19.5. Assessment of Safety

Safety will be evaluated by tabulations of adverse events (AEs), Cutaneous Safety Assessments for dryness and scaling, assessments for scores (erythema and telangiectasia) and Patient Global Impression of Treatment Side-Effects (PGI-SE) will be presented with descriptive statistics at Baseline and at Weeks 2, 4, 8 and 12 for each treatment group. Frequencies and percentages for each outcome category will be included in these statistics. Mean values will be presented graphically by week and treatment group.

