8.1.3 Visit Windowing

Data will be summarized based on nominal visit indications with the exception of data captured at early termination and unscheduled visits. Data from early termination and unscheduled visits will be summarized based on mapped visit values. The analysis windows for early termination and unscheduled visits are presented in the following table.

Analysis Windows for Efficacy and Safety Assessments

Scheduled Visit	Target Study Day	Window (Days)
Week 2	15	8 to 21
Week 4	29	22 to 42
Week 8	57	43 to 70
Week 12	85	71 to 98

Data collected at early termination and unscheduled visits prior to study day 8 will not be analyzed, with the exception of those identified as Baseline values. Data collected at early termination and unscheduled visits after study day 98 will not be included in analyses.

The definition for the study day included in each study window is defined as below:

Study Day prior to Day 1 = Visit Date – Day 1 Date

Study Day on or after Day 1 = Visit Date – Day 1 Date + 1

If an assessment's mapped visit is a visit at which the subject has data from a scheduled visit present, or if no analyses are planned for the assessment at the mapped visit, the data collected at the early termination or unscheduled visit will not be included in analyses.

In the event of multiple values from unscheduled or early termination assessments within an analysis window, the value closest to the scheduled visit target study day will be used for analyses. If two values tie as closest to the time point (for example, one value is before and the other value is after the time point), then the later value will be selected.

Data collected at all visits will be included in the data listings with visit presented as reported by the site.

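### Dryness, scaling, itching and burning/stinging are summarised by visit only, so no between-arm table shows each patient's worst grade at any time in the trial

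*SAP*

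**What the plan says.** Protocol section 8 lists as a safety endpoint the "Investigator Cutaneous Safety Assessment and Local Tolerability Assessments score at any time during the trial". Sections 16.1 and 16.2 call for scoring at Baseline and at "site visits at Weeks 2, 4, 8 and 12 (End of Study) or unscheduled visits".

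The planned summaries are all by visit:

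- Protocol 19.5 says that the dryness and scaling assessments "will be presented with descriptive statistics at Baseline and at Weeks 2, 4, 8 and 12 for each treatment group"; the synopsis has "will be presented with descriptive statistics at Baseline and at the scheduled study visits".
- SAP 8.8.4.1 (dryness, scaling) and 8.8.4.2 (itching, burning/stinging) plan descriptive statistics by arm and visit.
- The shell of Table 14.3.1.1 has rows for Baseline and Weeks 2, 4, 8 and 12, and no worst-grade or any-time row.

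SAP 8.1.3 governs which scores reach those rows, with windows labelled as applying to both efficacy and safety:

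- "Data collected at early termination and unscheduled visits prior to study day 8 will not be analyzed", apart from Baseline values. Scores after Day 98 are also left out.
- If the mapped visit already has scheduled data, "the data collected at the early termination or unscheduled visit will not be included in analyses".
- If several such scores fall in one window, "the value closest to the scheduled visit target study day will be used for analyses".
- "Data collected at all visits will be included in the data listings with visit presented as reported by the site".

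**The concern.** The safety objective (Protocol section 8, SAP 5.3) is to compare with vehicle how often these local reactions occur and how severe they are. The natural reading for a topical product is per patient: how many patients in each arm ever reached a moderate or severe grade. The planned tables do not answer that, for two reasons.

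First, by-visit counts cannot be added across visits to give patients. Second, scores taken between scheduled visits, which are the ones most likely to be prompted by a reaction, mostly do not reach the tables. Itching and burning/stinging are graded over the preceding 24 hours (Protocol 16.2), so an episode that has settled leaves no trace at the next scheduled visit. An unscheduled score may be its only graded record.

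The SAP already counts each patient once, at highest severity, for adverse events (8.8.2). The four reactions that are largely kept out of adverse event reporting get no equivalent.

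**Working it through.** The plan gives no figure on this point to reproduce. The check is of the windowing rule, of what by-visit counts can tell a reader, and of what the other outputs cover.

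**1. Do the windows leave any gap?** SAP 8.1.3 gives Days 8–21, 22–42, 43–70 and 71–98. Their lengths are 14 + 21 + 28 + 28 = 91 days, and Days 8–98 are 98 − 8 + 1 = 91 days. Each window starts the day after the previous one ends, so every day from 8 to 98 maps to exactly one visit.

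**2. Patient with all four scheduled scores.** An unscheduled score falls in one of three places:

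- before Day 8: excluded, unless it is the Baseline value;
- Days 8–98: maps to a visit with a scheduled score, so excluded;
- after Day 98: excluded.

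Applying the rule to each day from 2 to 130 gives no day on which a post-baseline unscheduled score enters the tables.

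**3. Patient with a scheduled score missing.** An unscheduled or early-termination score can enter only in the empty window: Days 8–21 for Week 2, 22–42 for Week 4, 43–70 for Week 8, 71–98 for Week 12. If there are several, the one nearest the target day is taken, whatever its grade. An early-termination score can also be displaced: with Week 4 seen on Day 29 and termination on Day 38, both fall in Days 22–42 and the later score is not tabulated.

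**4. What by-visit counts imply.** Suppose k patients in an arm have grade 2 or worse at each of the four post-baseline visits. If they are the same patients each time, k patients were ever affected; if they are all different, 4k were. The range k to 4k concerns scheduled scores only. Unscheduled scores could add patients beyond 4k.

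Illustration with assumed counts, on the planned arm sizes of 234 and 117:

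| Arm | At each visit | Ever affected, lowest | Ever affected, highest (scheduled scores) |
|---|---|---|---|
| Active | 12/234 = 5.1% | 12/234 = 5.1% | 48/234 = 20.5% |
| Vehicle | 6/117 = 5.1% | 6/117 = 5.1% | 24/117 = 20.5% |

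Equal by-visit rates in the two arms would thus be compatible with any per-patient rate from 5.1% to 20.5% in either arm. These are logical extremes, not expected values.

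**5. What the other outputs cover.** Under Protocol 16.1 and 16.2 these four reactions become adverse events only if they lead to temporary interruption of the product, discontinuation from the study, or a new medication. Those cases are in the adverse event tables, on the adverse event severity scale and not the 0–3 local grade. Listing 16.2.7.1 shows every score, but by subject. No planned table or figure gives a worst or any-time local grade by arm. SAP section 10, which lists changes to the planned analyses, records no decision to drop the any-time endpoint.

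**The case against.** The strongest reply is that nothing was promised and little is lost. The any-time phrase follows an adverse event bullet with the same wording and can be read as the observation period; neither document says worst or maximum. Protocol 19.5 and the synopsis plan by-visit summaries, SAP 7.2 lists the assessments without the phrase, and SAP section 2 gives the SAP precedence. The windowing rule simply gives one value per patient per visit. A patient who stops because of a local reaction is an adverse event by rule, whatever happens to the early-termination score. The listing is grouped by arm, so a determined reader could count worst grades.

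Much of this stands:

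- A reader might infer that SAP 8.1.3 is itself an error. It is not: the rule is normal for by-visit tables, and the gap lies in 8.8.4.1 and 8.8.4.2.
- A reader might infer that local safety data are lost or that serious reactions could go unseen. The documents do not support that: all scores are listed, and reactions that led to action are tabulated as adverse events.
- A worst post-baseline grade taken alone would count symptoms already present at Baseline as reactions. The fix has to allow for this.

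What the reply does not remove is the stated aim of comparing severity and frequency with vehicle. A by-subject listing is not a between-arm summary, and the adverse event tables leave out reactions that needed no action.

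**Conclusion.** The concern holds as a gap in the planned summaries. The endpoint is stated over the whole trial and scored at unscheduled visits, yet no between-arm summary of the worst local grade per patient is planned. The gap mainly affects transient reactions that led to no interruption, discontinuation or new medication.

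Its size in patients cannot be derived, because the documents give no rate of unscheduled or early-termination visits. Counting the calendar days on which a score would be excluded describes the rule; it does not measure how many patients are affected. The k to 4k range is exact for equal counts at four visits, but covers scheduled scores only, and the 12 and 6 in the illustration are assumed.

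The effect is probably modest: SAP section 4 reports that the Phase 2 formulations were well tolerated, with moderate local irritation in only a few patients. No efficacy result is touched. Minor; a cheap improvement.

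**What to change.** Keep the windowing rule for the by-visit and efficacy tables.

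1. **SAP 8.8.4.1 and 8.8.4.2.** For dryness, scaling, itching and burning/stinging, summarise by arm the worst post-baseline grade (0–3) over all assessments after first application: scheduled, unscheduled and early termination, including before Day 8. Give also the number and percentage of patients whose worst grade exceeds their Baseline grade. The denominator is Safety population patients with at least one such score; for the comparison with Baseline they also need a Baseline score.
2. **SAP 8.1.3.** State that its exclusions do not apply to this summary.
3. **Table 14.3.1.1.** Add the block, and beside it the worst grade over scheduled visits only and the number of patients per arm with any unscheduled score.

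The block is descriptive, with no test. It needs no new data and uses no alpha; the scores are already collected and listed. The cost is a few SAP sentences and one table block. The downside is that unscheduled visits are prompted by events and may differ in frequency between arms; the scheduled-only column and the count of patients with unscheduled scores make this visible.

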8.1.4 Adjustments for Covariates

Baseline lesion count will be a covariate for the primary efficacy endpoint for lesion counts. No other covariates are planned to be used in the analyses for this study.

8.1.5 Handling of Dropouts or Missing Data

Missing data for the ITT population will be estimated by multiple imputation and subsequently analyzed. Missing lesion count and IGA data will be derived for the analysis using the method of Markov Chain Monte Carlo (MCMC) multiple imputation. The pattern of missing observations in each treatment group cannot influence the missing value estimation in the other group because the imputation will be conducted independently for each treatment group.

Last observation carried forward (LOCF) will be used to impute missing data for the efficacy analyses using the PP population.

Patients that discontinue from the study due to an AE related to study treatment or documented lack of treatment effect will be included in the PP population. Data for these subjects will not be imputed by multiple imputation or LOCF but rather their data will be imputed with values consistent with their status as treatment failures. For these subjects, values for lesion count and IGA will be imputed such that change from Baseline is zero, meaning the values will be set to the Baseline value. This imputation will be done after the data for all subjects has been through the MI process.

Incomplete start and end dates for medications will be imputed. Other safety data will not be imputed and will be summarized on an observed case basis.

8.1.5.1 Lesion Count Variable Missing Data Imputation

Multiple imputation and subsequent analysis will involve 3 distinct phases with these principal tasks:

1. Create a data set of patients, one for each treatment group, with observed values and those needing estimation by MCMC. The missing lesion count values in each data set will be filled in using the MCMC method 5 times to generate 5 data sets. The resulting data sets for each treatment arm will be combined into one complete data set for each imputation.

Syntax:

```
proc mi data=datain out=dataout seed=&seed. nimpute=5 <options>;  
  where trtpn=(1, or 2);  
  mcmc chain=multiple;  
  var baseline week2 week4 week8 week12;  
run;
```

2. For each complete data set, the variable of interest for Baseline minus the value for the week imputed will be computed. Each complete data set will be analyzed as specified for the particular analysis.
3. The results from these analyses will be combined into a single inference using SAS PROC MIANALYZE.

A total of 2 random seeds are needed to impute inflammatory lesion counts. These random seeds have been pre-specified by using a random number generator:

- Inflammatory Lesion Counts S5G4T-1: Seed = 1787019983
- Inflammatory Lesion Counts Vehicle: Seed = 814066626

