8.1.5.2 IGA Missing Data Imputation

A similar procedure will be used for the analyses based on proportion of IGA successes wherein the ANCOVA analysis is replaced with a logistic regression analysis. Specifically, missing IGA values from which the dichotomized IGA is derived will be estimated by MCMC.

The pattern of missing observations in each treatment group cannot influence the missing value estimation in the other because the imputation is being conducted independently for each treatment group.

The missing IGA values will be derived for the analysis using the method of MCMC multiple imputation. Multiple imputation and subsequent analysis will involve 3 principal tasks:

1. Create a data set, one for each treatment group, of patients with observed values and those needing estimation by MCMC. The missing IGA values in each data set will be filled in using the MCMC method 5 times to generate 5 data sets. The resulting data sets for each treatment arm will be combined into one complete data set by imputation.

Syntax:

```
proc mi data=datain out=dataout seed=&seed. nimpute=5 <options>;  
  where trtpn=(1, or 2);  
  mcmc chain=multiple;  
  var baseline week2 week4 week8 week12;  
run;
```

2. For each complete data set, the dichotomous success rate (clear or almost clear) will be computed. The estimated global values will be rounded to the nearest integer value prior to evaluating the success rate. Each complete data set will be analyzed with a logistic regression with factors of treatment group and analysis center.
3. The results from these analyses will be combined into a single inference using SAS PROC MIANALYZE.

A total of 2 random seeds will be needed to impute IGA for the two treatment groups. Those 2 random seeds have been pre-specified by using a random number generator:

- IGA Week S5G4T-1: Seed = 325011659
- IGA Week Vehicle: Seed = 1440479769

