8.1.8 Multiple Comparisons/Multiplicity

In testing the secondary efficacy endpoints the overall Type I error will be controlled by requiring the two co-primary efficacy endpoints to be statistically significant. Specifically, failure of either one of the primary efficacy endpoints will invalidate the statistical significance of the secondary efficacy endpoints.

A stepwise process will be conducted for testing the secondary efficacy endpoints in order to control for multiplicity. These tests will be performed for only the ITT population. The testing process will terminate whenever a statistical test for a step is not significant. All subsequent tests for the remaining steps will be considered not significant. The order of testing is provided below.

Step Number	Secondary Endpoint
1	Percent change in inflammatory lesion count from Baseline to Week 12
2	Absolute change in inflammatory lesion count from Baseline to Week 8
3	Proportion of patients with the primary measure of success “Clear” (0) or “Almost clear” (1) in the IGA relative to Baseline at Week 8
4	Absolute change in inflammatory lesion count from Baseline to Week 4
5	Proportion of patients with the primary measure of success “Clear” (0) or “Almost clear” (1) in the IGA relative to Baseline at Week 4

In testing the supportive efficacy endpoints, the overall Type I error will be controlled by the Benjamini-Hochberg method. The Hochberg and Benjamini adaptive step-down Bonferroni method will be used within PROC MULTTEST in SAS (AHOLM option in PROC MULTTEST).

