8.7.3 Secondary Efficacy Analysis

Appropriate descriptive statistics will be computed for all secondary efficacy parameters.

The percent change from Baseline to Week 12 in inflammatory lesion counts and the absolute change from Baseline in inflammatory lesion counts at Week 8 and Week 4 will be analyzed using the same ANCOVA method described for the primary endpoint.

The proportion of subjects who are dichotomized to success (“clear” or “almost clear”) at Week 8 and Week 4 will be analyzed using the same logistic analysis method described for the co-primary endpoint.

A stepwise process will be conducted for testing the secondary efficacy endpoints in order to control for multiplicity, refer to Section 8.1.8.

The secondary efficacy analysis will be presented on only the ITT population.

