The protocol describes imputing only Week 12 data with MCMC imputation, but all missing post-baseline data will be imputed. Only 2 seeds are needed for the MCMC imputation for inflammatory lesions (one seed for S5G4T-1 and one seed for vehicle) instead of the 6 seeds that are given in the protocol. Only 2 seeds are needed for the MCMC imputation for IGA (one seed for S5G4T-1 and one seed for vehicle) so only one seed was given in the SAP. Using only the Week 12 seed addresses concern from the FDA with regard to imputing data at each visit as the multiple seeds in the protocol suggests. Only one seed is needed for treatment group as PROC MI will impute data across the visits.

All seeds given in the SAP were produced in SAS as seeds given in the 54-02 protocol were identical to the 54-01 study protocol.

Geographic region was removed from the examination of subgroups as all sites in the study are in the United States.

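### With only 5 imputations, both co-primary p-values and all five gated secondary p-values depend noticeably on the random seed.

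*SAP*

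**What the plan says.** For lesion counts, SAP 8.1.5.1 has missing values "filled in using the MCMC method 5 times to generate 5 data sets", separately by arm, and the results are "combined into a single inference using SAS PROC MIANALYZE". For IGA, SAP 8.1.5.2 says: "The missing IGA values in each data set will be filled in using the MCMC method 5 times to generate 5 data sets". Both code blocks carry nimpute=5. Seeds are fixed in advance, one per arm and variable, for example "Inflammatory Lesion Counts S5G4T-1: Seed = 1787019983" and "IGA Week S5G4T-1: Seed = 325011659".

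This is the ITT missing-data method (SAP 8.1.5), so it governs both co-primaries. It also reaches the secondaries, which are analysed on ITT only. Section 10 states that "all missing post-baseline data will be imputed", so Weeks 4 and 8 come from the same imputations, and under 8.7.3 the lesion-count secondaries "will be analyzed using the same ANCOVA method described for the primary endpoint". The IGA secondaries likewise reuse the co-primary logistic model.

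On multiplicity, SAP 8.1.8 requires both co-primaries to succeed before any secondary counts, and then: "The testing process will terminate whenever a statistical test for a step is not significant".

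The two multiple-imputation sensitivity analyses (SAP 8.7.2.1 and 8.7.2.2) and Protocol 19.4.7 and 19.4.8 also use 5. Neither document justifies the number, states an expected missing fraction, or plans a check of Monte Carlo error.

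**The concern.** The pooled estimate from m imputations is itself a random quantity: another seed gives another estimate, standard error and p-value. With m = 5 the estimate is an average of five draws, and the between-imputation variance is estimated on 4 degrees of freedom. Seven tests (two co-primaries and five secondaries) are then judged against a fixed 0.05 line from one run. If an endpoint lands near that line, the seed can decide it. A lost co-primary invalidates every secondary, and a lost secondary closes every later step.

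The same imputed data sets also supply the averaged skewness p-value that selects the ranked or unranked ANCOVA at 0.01 (SAP 8.7.1.1; footnote to Table 14.2.1.2) and the interaction test at 0.10 that can change the model. The seed can therefore influence which analysis is primary as well as its p-value.

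Two sets of seeds are already on record. Protocol 19.4.7.1 gives 2046620966 and 693843173 for Week 12 lesion counts; the SAP gives 1787019983 and 814066626, because the protocol's seeds duplicated those of a sister study (Section 10). Someone re-running the primary analysis with the protocol's seeds could get a visibly different p-value.

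**Working it through.** **Inputs.** From the documents: m = 5; two-sided 0.05; 234 active and 117 vehicle; Week 12 IGA success 53.3% vs 20.0%; lesion change -14.1 vs -7.4 with SDs 6.70 and 17.24 (SAP 9). Not in the documents, so assumed: the fraction of missing information (FMI) at 5%, 10% and 20% for the formula, and Week 12 missingness of 5% to 20% for the simulation.

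**The plan's own figures.** The plan gives no Monte Carlo error to reproduce; its only related figures are for power. A continuity-corrected test of two proportions at 95% power and 2:1 allocation needs 86 and 43, as stated. An unequal-variance t-test at 200/100 has standard error sqrt(6.70²/200 + 17.24²/100) = 1.79 and power 96.0%, against the stated 95%. At 234/117, power is about 98% for lesions and above 99.9% for IGA.

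**Formula.** Across seeds, the pooled estimate varies around its many-imputation value with variance B/m, where B is the between-imputation variance. Dividing by the total variance gives FMI/m, so

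SD of z across seeds ≈ sqrt(FMI/m).

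For FMI 10% and m = 5: sqrt(0.10/5) = 0.141. Then z = 1.96 + 0.141 = 2.101 gives p = 0.036, and z = 1.96 - 0.141 = 1.819 gives p = 0.069.

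| FMI | m = 5: SD; p at ±1 SD | m = 50 | m = 100 |
|---|---|---|---|
| 5% | 0.100; 0.039–0.063 | 0.032; 0.046–0.054 | 0.022; 0.047–0.053 |
| 10% | 0.141; 0.036–0.069 | 0.045; 0.045–0.055 | 0.032; 0.046–0.054 |
| 20% | 0.200; 0.031–0.078 | 0.063; 0.043–0.058 | 0.045; 0.045–0.055 |

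Over the central 95% of seeds, the m = 5 ranges are 0.031–0.078, 0.025–0.092 and 0.019–0.117.

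**Simulation.** Trials of 234/117 were imputed by multivariate-normal MCMC within arm over baseline and Weeks 2, 4, 8 and 12. They were analysed by ANCOVA or logistic regression with analysis center and pooled by Rubin's rules. For each data set, 600 imputations were generated and resampled 2,000 times at each m. Monotone dropout completely at random and between-visit correlations of 0.35 to 0.75 were assumed. Results below are for a many-imputation p of 0.04.

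| Endpoint, missing at Week 12 | m = 5: central 95% of p | Seeds with p > 0.05: m = 5 | m = 20 | m = 50 | m = 100 |
|---|---|---|---|---|---|
| Lesions Week 12, 5% | 0.029–0.058 | 12% | 0.2% | 0% | 0% |
| Lesions Week 12, 10% | 0.023–0.069 | 22% | 4% | 0.4% | 0% |
| Lesions Week 12, 20% | 0.018–0.093 | 38% | 14% | 3% | 0.4% |
| IGA Week 12, 5% | 0.029–0.057 | 10% | 0.7% | 0% | 0% |
| IGA Week 12, 10% | 0.022–0.081 | 28% | 9% | 1.6% | 0% |
| IGA Week 12, 20% | 0.017–0.10 | 36% | 16% | 4% | 0.4% |
| Lesions Week 4, 10% | 0.027–0.059 | 14% | 0.9% | 0% | 0% |

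**Cross-check.** FMI is smaller than the missing fraction because earlier visits inform the imputation: 10% missing gave FMI of about 5.3% (lesions) and 6.5% (IGA), and 20% missing gave about 11% and 13%. For lesions at 10% missing, the formula's SD is sqrt(0.053/5) = 0.103. A p of 0.04 is z = 2.054, which is 0.094 above 1.96. Then 0.094/0.103 = 0.91 SD, or about 18% of seeds crossing. The simulated 22% also includes seed noise in the variance estimate, which the formula omits.

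**Effect of about the planned size.** For Week 12 lesions with 10% missing and m = 5, p ran from 9e-07 to 2.3e-05 across seeds. In all planned-effect runs, no seed gave p above 0.05.

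**The case against.** The tests as planned are valid. Seeds are pre-specified, so there is no choosing among them, and type I error is not inflated. Rubin's rules already allow for small m: the reference degrees of freedom are roughly 4/FMI², or 4/0.10² = 400 at FMI 10% and 4/0.20² = 100 at 20%, giving critical values of 1.97 and 1.98. The 4 degrees of freedom behind the between-imputation variance therefore cost almost nothing in the reference distribution. Relative efficiency at FMI 10% is 1/(1 + 0.10/5) = 0.98.

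The co-primaries have ample planned power, and significance changes only for a result close to 0.05. The size rests on a missing fraction that the documents do not give, and the plan tries to keep it low by asking early terminators to complete the Week 12 procedures. The repeated-measures and GEE sensitivity analyses and the per-protocol analysis with LOCF do not depend on a seed and could expose a fragile co-primary. Even 20 imputations would remove most of the problem.

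All of this stands, and it limits how often the issue will matter. It does not remove it. Planned power is given only for Week 12, from a Phase 2 study with 30 to 32 patients per arm, while SAP 9 expects a more severe population. The Week 4 and Week 8 steps have no stated power. The seed-free sensitivity analyses cover the co-primaries only and do not replace the primary p-value. Pre-specifying a seed prevents manipulation but leaves the result just as arbitrary.

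**Conclusion.** The concern holds. At m = 5 the seed alone gives the pooled z an SD of 0.10 to 0.20 for assumed FMI of 5% to 20%. For a Week 12 result whose many-imputation p is 0.04, roughly 10% to 38% of seeds would report non-significance as missingness rises from 5% to 20%; Week 4 is affected less (14% of seeds at 10% missing). At 50 imputations these Week 12 shares fall to about 4% or less, and at 100 to 0.4% or less.

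The sizes depend on assumed missingness, dropout completely at random and assumed between-visit correlations. Under those correlations an FMI of 20% would need more than 20% missing at Week 12. The defect is one of precision and reproducibility and leaves the tests valid. The change should be made because the noise is avoidable.

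**What to change.** Set nimpute=100 (50 at the least) in the code and matching prose of SAP 8.1.5.1, 8.1.5.2, 8.7.2.1 and 8.7.2.2, keeping the SAP seeds. Report the Monte Carlo error of each pooled estimate and p-value. Record the change in SAP Section 10.

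Protocol 19.4.7.1, 19.4.7.2, 19.4.8.1 and 19.4.8.2 also say 5. The SAP Preface lets the SAP prevail and be updated before unblinding, but says an amendment will be considered for major differences such as changes to the primary-endpoint analysis, so the sponsor should document that decision.

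Estimand, models, alpha, testing order and seeds stay the same. The cost is one number in four code blocks, the accompanying text, and trivial computing time for about 351 patients.
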